8.1.2 Pulse Oximetry

Pulse oximetry measurements will be performed to evaluate SpO₂ as outlined in the SoA (Table 1-1) and in accordance with the site standard operating procedures, on a medical-grade medical device. Measurements will be taken with a probe on fingertip, toe or earlobe and recorded as percent oxygenated hemoglobin. Supplemental oxygen used at the time of assessment and method of oxygen delivery will be collected and documented along with the SpO₂.

Prior to administration of study intervention, supplemental oxygen will be held for at least a minute and SpO₂ checked in order to ensure participant may safely receive the study intervention. For safety reasons, since due to the current pandemic it cannot be guaranteed that study intervention will be consistently administered under direct clinical supervision, the study Investigators should provide study personnel who are able to monitor the participant and their SpO₂ and ensure that should it decrease to a threshold, this would trigger immediate discontinuation. By default, unless overruled by the study Investigator, this SpO₂ threshold is set to 89%. This threshold should be entered into the saturation monitoring device to trigger an alarm during nebulization.

FiO₂ will be measured per site standard practice and recorded in the eCRF. The device used to administer oxygen should also be recorded.

8.1.3 National Early Warning Score (NEWS) 2

The NEWS 2 will be measured prior to study intervention in the morning according to the SoA in Table 1-1.

The NEWS is based on a simple aggregate scoring system in which a score is allocated to physiological measurements, already recorded in routine practice, when patients present to, or are being monitored in hospital (RCP, 2012). Six simple physiological parameters form the basis of the scoring system:

1. Respiration rate

2. Oxygen saturation
3. Systolic blood pressure
4. Pulse rate
5. Level of consciousness or new confusion*
6. Temperature

**The patient has new-onset confusion, disorientation and/or agitation, where previously their mental state was normal – this may be subtle. The patient may respond to questions coherently, but there is some confusion, disorientation and/or agitation. This would score 3 or 4 on the Glasgow Coma Scale (rather than the normal 5 for verbal response), and scores 3 on the NEWS system.*

A score is allocated to each parameter as they are measured, with the magnitude of the score reflecting how extremely the parameter varies from the norm (zero for ‘normal’; maximum score 3). The score is then aggregated. The score is increased by 2 points for people requiring supplemental oxygen to maintain their recommended oxygen saturation. This is a pragmatic approach, with a key emphasis on system-wide standardization and the use of physiological parameters that are already routinely measured in National Health Service (NHS) hospitals and in prehospital care, recorded on a standardized clinical chart – the NEWS 2 chart (Refer to Appendix 2: The NEWS 2 Scoring System).

Reproduced from: Royal College of Physicians. National Early Warning Score (NEWS) 2: Standardising the assessment of acute-illness severity in the NHS. Updated report of a working party. London: RCP, 2017 (RCP, 2017).

8.2 Safety Assessments

Planned time points for all safety assessments are provided in the SoA (Table 1-1).

8.2.1 Physical Examinations

A complete physical examination will include, at a minimum, assessments of the head/ear/eyes/nose/throat, cardiovascular, respiratory, gastrointestinal, lymphatic, skin and neurological systems. Height (screening only) and weight will also be measured and recorded.

A brief physical examination will include, at a minimum, assessments of the skin, lungs, cardiovascular system, and abdomen (liver and spleen).

8.2.2 Vital Signs

Vital signs to be collected as outlined in the SoA (Table 1-1) and include body temperature, heart rate, blood pressure, and respiratory rate.

Body temperature will be assessed per the local practice (temporal or otic are preferred sites), and site will be recorded. Pulse rate, respiratory rate, and blood pressure will also be assessed per site SOC. Where possible the same methods should be used throughout the study for an individual participant.

Blood pressure and pulse measurements should be preceded by at least 5 minutes of rest for the participant in a quiet setting without distractions (e.g., television, cell phones). During study intervention administration, an alarm threshold should be set for heart rate at 120 beats/min (or as indicated by the Investigator), as outlined in the SoA (Table 1-1).

8.2.3 Electrocardiograms

Single 12-lead ECG will be obtained as outlined in the SoA (Table 1-1) using an ECG machine that automatically calculates the heart rate and measures PR, QRS, QT, and QTcF intervals for local reading.

8.2.4 Clinical Safety Laboratory Assessments

Refer to Appendix 3 for the list of clinical laboratory tests to be performed and to the SoA (Table 1-1) for the timing and frequency.

The Investigator must review the laboratory report, document this review, and record any clinically relevant changes occurring during the study in the AE section of the CRF. The laboratory reports must be filed with the source documents. Clinically relevant abnormal laboratory findings are those which are not associated with the underlying disease, unless judged by the Investigator to be more severe than expected for the participant's condition.

All laboratory tests with values considered clinically abnormal during participation in the study or within 4 days after the last dose of study intervention should be repeated until the values return to normal or baseline or are no longer considered clinically significant by the Investigator or Medical Monitor.

- If such values do not return to normal/baseline within a period of time judged reasonable by the Investigator, the etiology should be identified, where possible, and the Sponsor notified.

- All protocol-required laboratory assessments, as defined in Appendix 3, must be conducted in accordance with the Laboratory Manual and the SoA (Table 1-1).
- If laboratory values from laboratory assessments not specified in the protocol and performed at the institution's local laboratory result in the need for a change in participant management or are considered clinically relevant by the Investigator (e.g., are considered to be an SAE or an AE), then the results must be recorded in the CRF.

8.3 Adverse Events and Serious Adverse Events

The definitions of AEs and SAEs can be found in Appendix 4.

Adverse events will be reported by the participant (or, when appropriate, by a caregiver, surrogate, or the participant's legally authorized representative).

The Investigator and any qualified designees are responsible for detecting, documenting, and reporting events that meet the definition of an AE or SAE and remain responsible for following up AEs that are serious, considered related to the study intervention or the study, or that caused the participant to discontinue the study intervention (see Section 7).

8.3.1 Time Period and Frequency for Collecting AE and SAE Information

All AEs and SAEs will be collected from signing of informed consent until the last follow-up visit at the time points specified in the SoA (Table 1-1).

All SAEs will be recorded and reported to the Sponsor or designee within 24 hours of the Investigator becoming aware of the SAE, as indicated in Appendix 4. The Investigator will submit any updated SAE data to the Sponsor within 24 hours of it being available.

Investigators are not obliged to actively seek AEs or SAEs after the conclusion of study participation. However, if the Investigator learns of any SAE, including a death, at any time after a participant has been discharged from the study, and he/she considers the event to be reasonably related to the study intervention or study participation, the Investigator must promptly notify the Sponsor.

8.3.2 Method of Detecting AEs and SAEs

The method of recording, evaluating, and assessing causality of AEs and SAEs and the procedures for completing and transmitting SAE reports are provided in Appendix 4.

Care will be taken not to introduce bias when detecting AEs and/or SAEs. Open-ended and non-leading verbal questioning of the participant is the preferred method to inquire about AE occurrence.

8.3.3 Follow-up of AEs and SAEs

After the initial AE/SAE report, the Investigator is required to proactively follow each participant at subsequent visits/contacts. All SAEs will be followed until resolution, stabilization, until the event is otherwise explained, or the participant is lost to follow-up (as defined in Section 7.4). Further information on follow-up procedures is given in Appendix 4.

8.3.4 Regulatory Reporting Requirements for SAE

Prompt notification (within 24 hours, see Appendix 4) by the Investigator to the Sponsor of an SAE is essential so that legal obligations and ethical responsibilities towards the safety of participants and the safety of a study intervention under clinical investigation are met.

The Sponsor has a legal responsibility to notify both the local regulatory authority and other regulatory agencies about the safety of a study intervention under clinical investigation. The Sponsor will comply with country-specific regulatory requirements relating to safety reporting to the regulatory authority, Institutional Review Board (IRB)/Independent Ethics Committee (IEC), and Investigators.

Investigator safety reports must be prepared for suspected unexpected serious adverse reactions (SUSARs) according to local regulatory requirements and Sponsor policy and forwarded to Investigators as necessary.

An Investigator who receives an Investigator safety report describing an SAE or other specific safety information (e.g., summary or listing of SAE) from the Sponsor will file it along with the Investigator's Brochure and will notify the IRB/IEC, if appropriate according to local requirements.

8.3.5 Pregnancy

All women, including women of childbearing potential are allowed in the study. Urine pregnancy test will be performed on female participants of childbearing potential and pregnant females at screening. Females who are not of child bearing potential do not need to undergo a screening pregnancy test.

Pregnant females will be followed to determine the outcome of the pregnancy:

- The Investigator will collect any follow-up information on the participant and the neonate and the information will be forwarded to the Sponsor. Generally, follow-up will not be required for longer than 6 to 8 weeks beyond the estimated delivery date. Any termination of the pregnancy will be reported, regardless of fetal state (presence or absence of anomalies) or indication for the procedure.
- While pregnancy itself is not considered to be an AE or SAE, any pregnancy complication or elective termination of a pregnancy will be reported as an AE or SAE. Abnormal pregnancy outcomes (e.g., spontaneous abortion, fetal death, stillbirth, congenital anomalies, ectopic pregnancy) are considered to be SAEs. Any post-study pregnancy-related SAE considered reasonably related to study intervention by the Investigator will be reported to the Sponsor as described in Section 8.3.4. While the Investigator is not obligated to actively seek this information in former study participants, he or she may learn of an SAE through spontaneous reporting.

8.3.6 Disease-Related Events and/or Disease-Related Outcomes Not Qualifying as AEs or SAEs

The following disease-related events (DREs) are common in participants with COVID-19 and can be serious/life-threatening:

- Fever
- Cough*
- Dyspnea*
- Asthenia
- Loss of sense of taste and smell

** A cough or dyspnea episode related to study intervention administration does not meet the definition of a DRE and should be reported as an AE.*

Because these events are typically associated with the disease under study, they will not be reported as AEs.

NOTE: However, if either of the following conditions applies, then the event must be recorded and reported as an SAE (instead of a DRE):

- The event is, in the Investigator's opinion, of greater intensity, frequency, or duration than expected for the individual participant.

OR

- The Investigator considers that there is a reasonable possibility that the event was related to study intervention.

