Risk of clinical bronchial hyper-responsiveness related to nebulization	
Excipients in the nebulized RESP301 include mannitol which is a known bronchial irritant at the average dose of a positive mannitol test (239.0 ± 185.0 mg, Brannan et al, 2005). While the dose used in this study (54.66 mg) is lower than the average dose for a positive mannitol test, it has not yet been tested in COVID-19 patients and may potentially cause or exacerbate cough or bronchospasm in susceptible individuals in this specific population
	
Participants with a known history of moderate or severe bronchial hyperreactivity (such as in asthma) or presence of signs of significant bronchospasm on examination will be excluded from study participation (Exclusion criterion 5)
 
For the first 10 participants treated before the first Independent Data Monitoring Committee (IDMC) safety review (Section 9.6), RESP301 will be administered by intermittent inhalation until the intended dose is delivered (Section 6.1), so that the treatment can be quickly adjusted and rescue bronchodilator initiated if needed (Section 6.5.2)
 
After reviewing safety data, the IDMC will decide whether the intermittent inhalation of RESP301 can be replaced by continuous inhalation.

Potential Risk of Clinical Significance	Summary of Data/Rationale for Risk	Mitigation Strategy
Study Procedures		
Nebulization	The delivered dose of RESP301, estimated to be ~40% of the masses listed in Table 6-2, can be affected by patient technique and inspiratory capacity leading to inter- and intra-patient variation in actual doses of these ingredients, given the acute nature and high disease burden in this proposed clinical setting	Training will be provided to study staff to minimize variation in dose
Other		
Risk of spreading SARS-CoV-2	SARS-CoV-2 is known to be transmissible via respiratory droplets and any interventions that may potentially increase cough or aerosolization of respiratory secretions of an infected patient may increase risk of spread of disease	Proper personal protective equipment including appropriate mask, face shield, gown and gloves should be used at all times. When possible, the site staff should not remain in the room during study intervention administration (providing that continuous O ₂ monitoring can be conducted remotely and study intervention can be administered correctly)

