9.4.5.1 Adverse Events

Adverse Events will be coded using the MedDRA coding dictionary.

The number and percentage of participants with any AE, any related AE, any SAE, any related SAE, any severe AE, and related severe AE as well as the total number of events for each category will be summarized. The number of deaths due to an AE, hospitalization due to an AE, and study discontinuation due to an AE will be summarized.

The number and percentage of participants with an AE, as well as the total number of AEs, will be summarized by SOC and preferred term. This tabulation will be repeated for related AEs, SAEs, related SAEs, severe AEs, and related severe AEs.

All AEs will be provided in patient listings. Patient listings of AEs causing discontinuation of study medication, AEs leading to death, SAEs, related AEs, and severe AEs will be produced.

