10.4.1 Definition of AE

AE Definition

• An AE is any untoward medical occurrence in a patient or clinical study participant, temporally associated with the use of a study intervention, whether or not considered related to the study intervention.• NOTE: An AE can therefore be any unfavorable and unintended sign (including an abnormal laboratory finding), symptom, or disease (new or exacerbated) temporally associated with the use of a study intervention.

Events Meeting the AE Definition

• Any abnormal laboratory test results (hematology, clinical chemistry, or urinalysis) or other safety assessments (e.g., ECG, radiological scans, vital signs measurements), including those that worsen from baseline, considered clinically significant in the medical and scientific judgment of the Investigator (e.g., not related to progression of underlying disease).• Exacerbation of a chronic or intermittent pre-existing condition including either an increase in frequency and/or intensity of the condition.• New conditions detected or diagnosed after study intervention administration even though it may have been present before the start of the study.• Signs, symptoms, or the clinical sequelae of a suspected drug-drug interaction.• Signs, symptoms, or the clinical sequelae of a suspected overdose of either study intervention or a concomitant medication. Overdose per se will not be reported as an AE/SAE unless it is an intentional overdose taken with possible suicidal/self-harming intent. Such overdoses should be reported regardless of sequelae.• "Lack of efficacy" or "failure of expected pharmacological action" per se will not be reported as an AE or SAE. Such instances will be captured in the efficacy assessments. However, the signs, symptoms, and/or clinical sequelae resulting from lack of efficacy will be reported as AE or SAE if they fulfill the definition of an AE or SAE.

Events NOT Meeting the AE Definition

- Any clinically significant abnormal laboratory findings or other abnormal safety assessments which are associated with the underlying disease, unless judged by the Investigator to be more severe than expected for the participant's condition.
- The disease/disorder being studied or expected progression, signs, or symptoms of the disease/disorder being studied, unless more severe than expected for the participant's condition.

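### Cough and dyspnea within expectation can become AEs only in the RESP301 arm, so the any-AE, cough and dyspnea rows are not a valid between-arm comparison

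*Protocol*

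**What the plan says.** Protocol 8.3.6 lists fever, cough, dyspnea, asthenia and loss of taste and smell as disease-related events and states: "Because these events are typically associated with the disease under study, they will not be reported as AEs". For cough and dyspnea a footnote adds: "A cough or dyspnea episode related to study intervention administration does not meet the definition of a DRE and should be reported as an AE".

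A NOTE in the same section gives two conditions, either of which makes the event reportable as an SAE:
- "The event is, in the Investigator's opinion, of greater intensity, frequency, or duration than expected for the individual participant"
- "The Investigator considers that there is a reasonable possibility that the event was related to study intervention"

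Section 10.4.1 defines an AE as an occurrence "temporally associated with the use of a study intervention, whether or not considered related to the study intervention", but it excludes "expected progression, signs, or symptoms of the disease/disorder being studied, unless more severe than expected for the participant's condition".

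Section 9.4.5.1 plans the main AE table: "The number and percentage of participants with an AE, as well as the total number of AEs, will be summarized by SOC and preferred term". The tabulation is repeated for related AEs. The Safety Population (9.3) includes all participants randomized to control, and 9.4.1 has categorical variables summarized by treatment. Table 2-1 (2.2.1) says that the mannitol in RESP301 "may potentially cause or exacerbate cough or bronchospasm in susceptible individuals in this specific population".

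**The concern.** The main preferred-term table is meant to be free of attribution, since related AEs have their own table. For cough and dyspnea within expectation it is not: attribution to dosing decides whether the episode is recorded at all. That judgement is made open label, and only one arm receives the dosing to which an episode could be attributed.

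Two errors can follow. Attributed episodes can produce an active-arm excess when the true rates are equal. Conversely, a drug-caused worsening that the investigator reads as COVID-19, and still judges to be within expectation, is recorded in neither arm. At stake is the randomized comparison for cough, which the sponsor itself flagged, and for dyspnea.

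**Working it through.** The protocol states no figure to reproduce on this point. The check has two parts: following the recording rule through each arm, and showing what the resulting table could look like.

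**1. The rule by arm (8.3.6, 10.4.1, 4.1)**

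| Cough or dyspnea episode | RESP301 + SOC | SOC alone |
|---|---|---|
| Beyond expected intensity, frequency or duration | Reportable (SAE under the NOTE) | Reportable (SAE under the NOTE) |
| Within expectation, attributed to dosing | AE under the footnote; SAE under the NOTE | Cannot occur |
| Within expectation, not attributed | Not recorded as an AE | Not recorded as an AE |

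Only the first row is recorded on the same basis in both arms. The second row puts entries into the any-AE, cough and dyspnea rows for one arm only. The general AE definition in 10.4.1 gives controls no other route, because it too excludes expected symptoms of the disease.

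**2. Whether another planned summary supplies the comparison**

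Section 8.3.7 defines no AEs of special interest. The bronchial hyper-responsiveness endpoint in 9.4.5 is itself limited to nebulization-related events. The protocol describes no tabulation of disease-related events by arm.

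**3. Illustration of size**

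Inputs from the protocol: 200 and 100 participants (9.2). Inputs not in the documents, so assumed: true rate q of within-expectation cough or dyspnea, 20% to 60% and equal in both arms; share a of active-arm episodes attributed to dosing, 10% to 50%.

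Expected active-arm participants with a recorded episode = 200 × q × a. The control count is 0 by rule.

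| q | a = 10% | a = 25% | a = 50% |
|---|---|---|---|
| 20% | 4 v 0 | 10 v 0 | 20 v 0 |
| 40% | 8 v 0 | 20 v 0 | 40 v 0 |
| 60% | 12 v 0 | 30 v 0 | 60 v 0 |

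Under a rule that ignored attribution, the same equal rates would give 40/200 v 20/100, 80/200 v 40/100 and 120/200 v 60/100, each with a risk difference of 0.

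To gauge how such counts would look, the two-sided Fisher exact p for x/200 against 0/100 is:
- x = 6 (3%): 0.18
- x = 8 (4%): 0.056
- x = 9 (4.5%): 0.032, the smallest count below 0.05
- x = 10 (5%): 0.034
- x = 20 (10%): 0.0003

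The chance of 9 or more recorded participants, from a binomial with n = 200 and probability q × a, is 2% to 85% at a = 10%, 67% to over 99% at a = 25%, and over 99% at a = 50%, across the three values of q.

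**4. Error in the other direction**

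Assume a true excess of 15 points (45% v 30%). The table difference is 45% × a − 0, which is 4.5, 11.3 or 22.5 points at a = 10%, 25% or 50%. The displayed difference follows attribution and can fall below or above the true one.

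**The case against.** Leaving expected disease symptoms out of AE reporting is a deliberate convention, and the protocol (4.2) gives reduced site burden as its reason for having no blinding or placebo. Without placebo nebulization, a cough provoked by dosing has no control counterpart under any recording rule. Episodes beyond expectation are reportable in both arms. Bronchospasm is not on the disease-related list. Nebulization intolerance has its own endpoints, and untolerated worsening of cough is a listed discontinuation reason in 7.1. The schedule of activities also collects SpO₂, NEWS 2 and vital signs, so respiratory worsening does not rest on AE terms alone. An excess made only of attributed episodes would reappear in the related-AE table. Finally, no AE significance test is planned, and the counts above are assumed.

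All of this stands, and it limits the point. A reader might infer that the rule removes any comparison of the drug's main harm, or that every drug-caused worsening misread as COVID-19 is lost. The documents support neither. Table 2-1 names cough or bronchospasm alongside other risks such as methemoglobinemia and does not rank them, and worsening beyond expectation is recorded in either arm. A reader might also take the p-values as predictions of the trial's result; they only show how large the artefact could look.

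What the objection does not remove is the mixing of rules within one table. The related-AE table can expose a false excess but cannot recover episodes that were never recorded. A SAP could change the presentation, but it can use only what 8.3.6 allows to be collected.

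**Conclusion.** The point holds in a limited form. For cough and dyspnea within expected intensity, frequency and duration, the control AE count is zero by rule, while the active-arm count is whatever is attributed open label. The any-AE, cough and dyspnea rows of 9.4.5.1 are therefore not a valid between-arm comparison for these episodes.

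The one-arm recording follows from the text alone and needs no assumption. Its size does: it depends on an attribution rate and a true event rate that the documents do not give. Nine attributed participants of 200 would look nominally significant against none of 100; six would not.

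Separately, 8.3.6 contradicts itself. For an event related to study intervention, the footnote says AE and the NOTE says SAE. Which one applies decides which table these episodes enter.

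**What to change.** **Preferred, with no new data.** In 9.4.5.1, state that cough and dyspnea that are AEs only through the 8.3.6 footnote are reported separately, as active-arm nebulization tolerability, and are left out of the between-arm any-AE and preferred-term comparison. Keep in that comparison cough and dyspnea reported in either arm because they exceeded expectation. Dropping all disease-related terms would discard the only cough and dyspnea records made on the same basis in both arms. The cost is a short text change and a flag for the route by which each such event was reported.

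**Alternative.** At the AE reviews already scheduled in both arms, record new or worsened cough and dyspnea regardless of attribution, with relatedness as a separate field. Sections 8.3.6 and 10.4.1 must be amended together, because 10.4.1 excludes expected symptoms. A reference status for new or worsened is also needed, since the schedule of activities has no cough or dyspnea severity score. The cost is more non-serious AE entries. Ascertainment would still be open label, with the active arm observed at three dosings a day.

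**In either case.** Reconcile the footnote and the NOTE in 8.3.6 on whether a related event is reported as an AE or an SAE.
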